#### **6.1.6. Assignment of Adverse Events to Study Parts and Treatment Groups**

Each treatment-emergent adverse event by definition occurs within 3 days (with a possible extension if a second dose was taken in the OLE period) of a study drug dose. TEAEs will be assigned to study parts based on the dose they are thus associated with, i.e. TEAEs occurring after run-in or double-blind doses will be assigned to Part 1 and TEAEs occurring after OLE doses will be assigned to Part 2. TEAEs will also be assigned to the treatment group associated with the dose.

Non-treatment-emergent AEs will be assigned to study parts based on their onset date. Non-treatment-emergent AEs starting prior to the date of Visit 4 will be assigned to Part 1 and starting on or after the date of Visit 4 to Part 2. In case an AE has a partial start date that is ambiguous

and could have occurred either before or after the date of Visit 4, such AE will be assigned to Part 1. Non-treatment-emergent AEs will not be assigned to treatment groups.

### **6.1.7. Summaries of Adverse Events and Deaths**

TEAEs will be summarized based on the safety analysis set for Part 1 and based on the OLE analysis set for Part 2. All TEAEs will be summarized by body system, and by preferred terms within a body system, by severity, and by relation to study medication. Each AE (based on preferred terminology) is counted only once for a given subject within a specified treatment or study period. If the same AE occurred on multiple occasions, the highest severity and least complimentary relationship will be assumed. If two or more AEs were reported as a unit, the individual terms will be reported as separate AEs.

## **6.2. Laboratory Evaluations**

Laboratory data are collected at Screening, Visit 4, and at End of Study for this study. Laboratory data collected will be summarized using the safety analysis set for Part 1 and using the OLE analysis set for Part 2. The analysis will be based on both values reported in SI units and in conventional units. Summaries in conventional units will be provided only for those parameters, for which conventional unit are different from the SI units.

A by-subject listings for laboratory test results will be provided by subject ID number and time point in chronological order for hematology, chemistry, urinalysis, and urine drug test, and pregnancy test. Values falling outside the normal reference range will be flagged in the data listings, as appropriate.

No formal statistical testing is planned.

### **6.2.1. Summaries of Numeric Laboratory Results**

For Part 1, numeric laboratory results at Part 1 baseline and Visit4/End of Double-Blind Period as well as the change from baseline to end of double-blind period will be summarized using descriptive statistics (N, mean, standard deviation, median, minimum, and maximum) by treatment group.

For Part 2 numeric laboratory results will be similarly summarized for Part 2 baseline and Month 6 visit.

The proportion of subjects with Low (below the lower limit of normal range), Normal (within the limit of normal range), High (above the upper limit of normal range) will be presented for both parts.

### **6.2.2. Shifts Relative to the Baseline Value**

Shift tables will be presented by showing changes in results from Part 1 baseline value (low, normal, and high) to the End of Double-Blind for Part 1 and from Part 2 baseline value to End of Study (Month 6) for hematology, blood chemistry, and urinalysis.

### 6.2.3. Other Laboratory Results

A summary of pregnancy results (positive/negative) will be provided for postmenarcheal female subjects in the safety analysis set for Part 1 and the OLE analysis set for Part 2.

A summary of urine drug test results (positive/negative) will be provided for subjects in the safety analysis set who were 9 years of age or older at Screening for Part 1 and End of Double-blind period for Part 2. The reason(s) for the positivity will also be listed.

### 6.3. Vital Signs

Descriptive statistics of systolic blood pressure, diastolic blood pressure, heart rate, respiratory rate, and oral body temperature will be provided at every visit for both study parts. The change from the corresponding part baseline will be summarized similarly for post-baseline visits.

Additionally, vital signs will be summarized by periods in the Double-Blind phase of Part 1. Summary at the period baseline, end of period and change from baseline to end of period will be summarized by the treatment in that period (each ZNS dose level and Placebo). Period baseline will be defined as the last assessment taken prior to the treatment in each of the two Double-Blind periods. End of period is defined as the next scheduled assessment after the treatment.

Proportions of subjects with clinically significant vital signs will also be summarized. Clinically significant vital signs are defined in [Table 5](#).

**Table 5: Definitions of Potentially Clinically Significant Vital Signs**

Vital Sign	Criterion	Change from baseline
Systolic blood pressure	$\geq 131$ mmHg; $\leq 90$ mmHg	Increase and decrease $\geq 20$ mmHg
Diastolic blood pressure	$\geq 83$ mmHg; $\leq 46$ mmHg	Increase $\geq 30$ mmHg; Decrease $\geq 20$ mmHg
Pulse rate	$> 120$ bpm; $< 60$ bpm	Increase $\geq 15$ bpm; Decrease $\geq 15$ bpm
Temperature	$> 38.3^\circ\text{C}$	Change $\geq 1.11^\circ\text{C}$

### 6.4. Prior, Concomitant, and Rescue Medications

Prior and concomitant medications will be coded using the current version of World Health Organization (WHO) Drug Dictionary.

Prior medications are defined as medications taken and stopped prior to the first dosing date of study drug (placebo run-in). Concomitant medications for Part 1 are defined as medications taken while a subject took study drug in Part 1 or prior to taking study drug and continued during Part 1, up to Visit 4 date. Concomitant medications for Part 2 are defined as medications taken at any time on or after the date of Visit 4. Use of concomitant medications will be summarized by ATC Level 2 class, preferred name, study period, and within the Double-Blind period by treatment, using the number and percentage of subjects in the safety analysis set for Part 1 and in the OLE analysis set for Part 2. A subject reporting the same medication more than once in the same period will be counted only once when calculating the number and percentage of subjects

who received that medication. The summary will be ordered alphabetically by medication class (WHODrug ATC 2 Term) and preferred term (WHODrug Product term).

No formal statistical testing is planned for prior and concomitant medications.

Rescue medications are defined as those used after the study drug treatment for further alleviation of pain associated with the migraine attack, and is recorded on the subject's diary. Note: if subject diary includes records of rescue medication that started prior to the start of migraine, such medications will be ignored as incorrect diary entry. The use of rescue medication in Part 1 will be summarized by ATC Level 2 class, preferred name and treatment using the number and percentages of subjects in the safety analysis set. A subject reporting the same medication more than once will be counted only once when calculating the number and percentage of subjects who received that medication. The summary will be ordered alphabetically by medication class (WHODrug ATC 2 term) and preferred term (WHODrug Product term). The time to the use of rescue medication will also be summarized. Details are provided in Section 5.3.

## 6.5. Electrocardiogram Results

Descriptive statistics of ventricular rate, PR interval, QRS interval, QT interval, corrected QT intervals (QTcF and QTcB), and RR interval will be provided at Part 1 baseline and End of Double-Blind period for Part 1 for the safety analysis set and also for Part 2 baseline and End of Study (Month 6) for the OLE analysis set. Change from the corresponding part baseline for these parameters will also be summarized.

The QT interval (measured in millisecond [msec]) is a measure of the time between the start of the Q wave and the end of the T wave in the heart's electrical cycle. The QT interval represents electrical depolarization and repolarization of the ventricles. The QT interval is affected by heart rate, and a number of methods have been proposed to correct QT for heart rate.

Corrected QT (QTc) intervals will be derived using Fridericia's correction (QTcF) as follows:

$$QT_{cF} = \frac{QT}{\sqrt[3]{RR}}$$

where QT is measured in msec;  $RR = 60/\text{Heart Rate}$  (beats per min [bpm]) and RR is measured in seconds

Corrected QT (QTc) intervals will be derived using Bazett's correction (QTcB) as follows:

$$QT_{cB} = \frac{QT}{\sqrt{RR}}$$

where QT is measured in msec;  $RR = 60/\text{Heart Rate}$  (beats per min [bpm]) and RR is measured in seconds

ECG overall interpretation and rhythm assessment will also be summarized categorically by visit for both parts.

ECG results will also be summarized based on the following categories.

**Table 6: Definitions of Potentially Clinically Significant ECG Parameters**

ECG parameter	Criterion	Change from baseline
Heart rate	> 120 bpm; < 60 bpm	Increase $\geq$ 15 bpm; Decrease $\geq$ 15 bpm
PR	$\geq$ 200 msec	
QRS	$\leq$ 50 msec $\geq$ 100 msec	
QT	$\geq$ 500 msec $\leq$ 200 msec	Increase $\geq$ 60 msec
QTcB	$\geq$ 450 msec	Increase 15% from baseline
QTcF	$\geq$ 450 msec	Increase 15% from baseline

### 6.6. Columbia-Suicide Severity Rating Scale

Suicidal ideation will be defined as “yes” answer to any one of the five suicidal ideation questions (Question 1-5) on the C-SSRS.

Suicidal behavior will be defined as “yes” answer to any one of the 5 suicidal behavior questions (Actual attempt, Interrupted attempt, Preparatory Acts or Behavior, Suicidal behavior, Complete suicide) on the C-SSRS.

The frequencies and percentages of suicidal behavior and suicidal ideation from the Columbia Suicidal Severity Rating Scale (C-SSRS) will be summarized by randomized treatment and by visit and overall (at least once post-baseline) using the safety analysis set for Part 1, and also using the OLE analysis set for Part 2.

The frequencies and percentages of suicidal behavior and suicidal ideation will also be summarized by periods in the Double-Blind phase of Part 1. Summary at the period baseline and end of period will be summarized by the treatment in that period (each ZNS dose level and Placebo). Period baseline will be defined as the last assessment taken prior to the treatment in each of the two Double-Blind periods. End of period is defined as the next scheduled assessment after the treatment.

### 6.7. Physical Exam Results

The frequency distribution of abnormal physical findings at Part 1 baseline, and End of Double-Blind period will be tabulated for Part 1 using the safety analysis set, as well as at Part 2 baseline and at End of Study (Month 6) for Part 2 using the OLE analysis set.

## **6.8. Duration of the OLE Period**

Numbers and percentages of subjects who treated at least one migraine in each of the six OLE period months will be presented for the OLE Analysis Set by month, weight group and dose level. For the purposes of this summary, months will be defined as 30-days periods starting from the day of Visit 4.

Additionally, the counts and percentages meeting the following criteria will be presented:

- Subjects who completed all 6 months of the OLE period, i.e. those that completed the OLE period and had their Visit 6 at least 180 days after Visit 4
- Subjects who completed all 6 months of the OLE period and treated an average of at least 1 attack per month
- Subjects who completed all 6 months of the OLE period and treated an average of at least 1 attack per month and no more than 4 attacks in any month.

For this analysis subjects will be assigned to treatment groups based on the last dose they received in Part 2.

## **6.9. Changes From Protocol-Specified Safety Analyses**

There are no changes from the protocol-specified safety analyses.

## **7. SOFTWARE**

SAS® Software Version 9.4 or later. SAS Institute Inc., Cary, NC, USA.

## 8. CODE SAMPLES

### 8.1. Primary analysis GEE model

```
proc genmod data=...;
  class trtp aperiod trtseqp usubjid weightcat base;
  model avalc(event='Y') = trtp aperiod trtseqp weightcat base / dist=binomial
link=logit type3;
  repeated subject=usubjid(trtseqp) / type=UN within=aperiod;
  lsmeans trtp / diff cl oddsratio ilink;
run;
```

The input dataset needs to include a record per each subject/treatment period. Explanation of variables:

1. TRTP: planned treatment at the time of assessment
2. APERIOD: treatment period number (1 or 2)
3. TRTSEQP: planned sequence of treatments (ZNS-Placebo or Placebo-ZNS)
4. USUBJID: unique subject identifier
5. WEIGHTCAT: weight category (<50 kg or >=50 kg)
6. BASE: pre-dose headache severity
7. AVALC: response variable (Y = response achieved, N = not achieved).

Odds ratios, their confidence intervals and p-values will be found in the Diff's ODS dataset.

### 8.2. Sensitivity Analysis Logistic Regression

```
proc logistic data=...;
  where aperiod = 1;
  class trtp weightcat base / param=ref;
  model avalc(event='Y') = trtp weightcat base;
run;
```

The input dataset needs to include a record per subject from treatment period 1 only. The meaning of the variables is the same as in the primary analysis GEE model.

### 8.3. Sensitivity Analysis CMH Test

```
proc freq data=...;
  where aperiod = 1;
  tables sitegr1*trtp*avalc / cmh;
run;
```

The input dataset needs to include a record per subject from treatment period 1 only. The meaning of the variables TRTP and AVALC is the same as in the primary analysis GEE model. SITEGR1 is pooled site.

## 8.4. Sensitivity Analysis McNemar Test

```
proc freq data=...;
  by trtseqp;
  tables avalc1*avalc2 / agree;
run;
```

The input dataset needs to include a record per subject with variables:

- AVALC1: responses in treatment period 1
- AVALC2: responses in treatment period 2
- TRTSEQP: planned sequence of treatments (ZNS-Placebo or Placebo-ZNS)

## 8.5. Sensitivity Analysis Repeated Measures Model

```
proc genmod data=...;
  class trtp aperiod trtseqp usubjid weightcat base atptn;
  model avalc(event='Y') = trtp aperiod atptn trtp*atptn weightcat base/
  dist=binomial link=logit type3;
  repeated subject=usubjid(trtseqp) / type=UN within=aperiod*atptn;
  lsmeans trtp*atptn / diff cl oddsratio ilink;
run;
```

The input dataset needs to include a record per subject, period (1 or 2) and timepoint (0.5 hr, 1 hr, 2 hr or 24 hr post-dose).

The variables are the same as in the primary analysis GEE model, plus:

- ATPTN: timepoint number (0.5 hr, 1 hr, 2 hr or 24 hr post-dose).

In case of convergence problems type=AR(1) and type=EXCH will be tried.

## 8.6. Sensitivity Analysis with Multiple Imputations and Tipping-Point Analysis

**Step 1.** A dataset needs to be created with the following variables:

1. TRTP: planned treatment at the time of assessment
2. APERIOD: treatment period number (1 or 2)
3. TRTSEQP: planned sequence of treatments (ZNS-Placebo or Placebo-ZNS)
4. USUBJID: unique subject identifier
5. WEIGHTCAT: weight category (<50 kg or >=50 kg)
6. BASE: pre-dose headache severity
7. AVALC: response variable (Y = response achieved, N = not achieved).

The following rows need to be included:

1. Data for all subjects for the 2-hour timepoint in Period 1 with non-missing AVALC
2. Data for all subjects with missing AVALC for the 2-hour timepoint in Period 2. In these rows both BASE and AVALC will be missing.

**Step 2.** Use the dataset from Step 1 as input to perform logistic regression on Period 1 data and estimate the probability of response in Period 2:

```
proc logistic data=...;
  class trtp weightcat / param=ref;
  model avalc(event='Y') = trtp weightcat;
  output out=predicted p=pred_prob;
run;
```

In the output dataset PREDICTED the variable PRED\_PROB will indicate the predicted probability of response.

**Step 3.** To ensure results are repeatable and amenable to validation by double-programming, a seed value 2291601 will be used in all random number generation functions below. The value was chosen arbitrarily based on the protocol number.

For each value of penalization factor  $\Delta$  ranging from 0 to 1 in increments of 0.05 do the following.

For each subject with missing Period 2 result perform the following steps 25 times:

- Draw a random uniform variable,  $u$ , between 0 and 1 (i.e.  $u = \text{ranuni}(2291601)$ )
- If the subject receives ZNS in Period 2 and if the value of  $u < \text{PRED\_PROB} - \Delta$ , impute response (AVALC = 'Y'); otherwise, impute no response (AVALC = 'N'). This effectively penalizes the ZNS treatment by making it less likely to have a responder.
- If the subject receives Placebo in Period 2 and if the value of  $u < \text{PRED\_PROB}$ , impute response (AVALC = 'Y'); otherwise, impute no response (AVALC = 'N').
- Draw a random uniform variable,  $v$ , between 0 and 1 (i.e.  $v = \text{ranuni}(2291601)$ ).
- If  $v < 0.5$ , then impute pre-dose headache severity = 'SEVERE'; otherwise, impute pre-dose headache severity = 'MODERATE'.
- Add thus imputed data for Period 2 to actual, observed data from Period 2. As the result all subjects in the FAS must now have a result, observed or imputed, for Period 2
- Analyze the dataset obtained above using the same method as in the primary analysis (section 8.1)

**Step 4.** After the previous steps we obtain Diff's ODS dataset for each value of the penalization factor and each of the 25 multiple imputations. Within each penalization factor value combine the results of the multiple imputations:

```
proc mianalyze data=Diff's;
  by penalization_factor;
  modeleffects Estimate;
  stderr StdErr;
run;
```

The input dataset is the Diff's ODS dataset from the previous step.

**Step 5.** Convert the estimates to odds ratios using the following data step code on the ParameterEstimates ODS dataset from the previous step:

```
OddsRatio = exp(Estimate);
z = probit(1-0.05/2);
UpperOR = OddsRatio*exp(z*StdErr);
LowerOR = OddsRatio*exp(-z*StdErr);
```

These results will be presented in the table.

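### Section 8.6 Step 3, read literally, feeds the crossover model only Period 2 records, on which the treatment difference cannot be estimated

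*SAP*

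**What the plan says.** Section 8.6 of the SAP handles records as follows.

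- **Step 1** builds an input dataset from two kinds of row. The first is "Data for all subjects for the 2-hour timepoint in Period 1 with non-missing AVALC". The second is the Period 2 rows in which the 2-hour response is missing.
- **Step 2** fits a logistic regression to the Period 1 rows and predicts the probability of response for the missing Period 2 rows.
- **Step 3** imputes the missing Period 2 responses and predose severities, then instructs: "Add thus imputed data for Period 2 to actual, observed data from Period 2". The completeness check that follows names the same period: "As the result all subjects in the FAS must now have a result, observed or imputed, for Period 2". The next instruction is "Analyze the dataset obtained above using the same method as in the primary analysis (section 8.1").
- **Steps 4 and 5** pool the treatment differences from the imputed datasets with PROC MIANALYZE and convert them to odds ratios.

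Section 8.1 specifies the model as "model avalc(event='Y') = trtp aperiod trtseqp weightcat base / dist=binomial", with the within-subject structure "repeated subject=usubjid(trtseqp) / type=UN within=aperiod". It states its input as "The input dataset needs to include a record per each subject/treatment period".

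Sections 5.2.1.3 and 5.2.1.4 prescribe the primary analysis model for both analyses and make both conditional on a dropout rate above 20%.

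**The concern.** In section 8.6 the Period 1 records serve only to fit the imputation regression. The dataset that Step 3 describes and passes on contains imputed and observed Period 2 records and nothing else. The Step 1 dataset does not fill the gap: it holds Period 1 rows and the missing Period 2 rows, without the observed Period 2 rows, and Step 3 does not say to append to it.

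The section 8.1 model is a two-period crossover model. It separates treatment from sequence only because each child contributes a record under each treatment. With one period, that separation is lost. At stake are the plan's only imputation-based checks on missing data for the primary endpoint. They are called for when dropout is high, and as written their steps do not lead to a usable estimate.

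**Working it through.** **Inputs**

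- Fixed effects: treatment, period, sequence, weight category and predose severity, plus an intercept (section 8.1).
- Two sequences: "TRTSEQP: planned sequence of treatments (ZNS-Placebo or Placebo-ZNS"), allocated 1:1 (section 2.3).
- 240 high-dose subjects (section 1.2), so 120 per sequence. This only sizes the check.
- Assumption: weight category and predose severity split about 50:50. The SAP gives no such figures, and the aliasing does not depend on them.

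The SAP states no figure for this point, so there is none to reproduce.

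**Algebra.** Let s = 1 for placebo-then-ZNS and s = 0 for ZNS-then-placebo. Let t = 1 for ZNS and 0 for placebo. Write μ for the intercept, τ for treatment, π for Period 2 and σ for sequence, on the logit scale and leaving out the two covariates.

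- In Period 2, t = s, so the linear predictor is (μ + π) + (τ + σ)s. Only the sums μ + π and τ + σ are determined; τ alone is not.
- In Period 1, t = 1 − s, so the linear predictor is (μ + τ) + (σ − τ)s.
- With both periods, the slope in s is τ + σ in Period 2 and σ − τ in Period 1. Hence τ = [(τ + σ) − (σ − τ)] / 2, and the treatment effect is identified.

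**Rank count**

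- Both periods: intercept 1 + treatment 1 + period 1 + sequence 1 + weight 1 + severity 1 = 6.
- Period 2 only: period duplicates the intercept (−1) and treatment duplicates sequence (−1), so 6 − 2 = 4.

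**Numerical check of the full design matrix, all class levels included**

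| Dataset | Rows | Records per subject | Rank (6 needed) | Absolute correlation, treatment with sequence | ZNS − placebo estimable? |
|---|---|---|---|---|---|
| Period 2 only (Step 3 as worded) | 240 | 1 | 4 | 1.0 | No |
| Periods 1 and 2 | 480 | 2 | 6 | 0 | Yes |

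On the Period 2 dataset the difference requested by the `lsmeans` statement in section 8.1 lies outside the row space of the design. With one record per subject there is also no between-period pair from which to estimate the unstructured within-subject correlation. Step 4 pools exactly that difference, so it receives nothing valid. Restoring the Period 1 records removes both problems.

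**The case against.** The best defence is that the Step 3 sentence describes only how Period 2 is completed, and that the cross-reference to section 8.1 supplies the rest. Section 8.1 asks for a record per subject and period and lists period as 1 or 2, so a programmer who follows it would add Period 1. The literal run would also fail visibly, without returning a plausible wrong answer. Most of this stands: the intended dataset can be inferred, and the error is very probably an omission. It does not remove the point, because Step 3 gives an explicit data-construction rule, repeats Period 2 in its completeness check, and directs that this dataset be analysed. Followed exactly, it conflicts with the input section 8.1 requires.

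Three stronger readings are tempting and should be resisted.

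- A reader might infer that the analyses would become a weaker between-child comparison in Period 2, with lower power. That requires dropping sequence from the model, which no passage permits. Any power figure would also rest on response rates that the SAP does not give; section 1.2 states only a difference of 0.11 and a standard deviation of 0.5.
- A reader might infer that carryover would fall on the treatment effect because of this fault. That again presupposes the altered model, and unequal carryover can bias the ordinary two-period estimate too.
- A reader might see a contradiction with step c of section 5.2.1.3. That step calls for the primary model and is silent on which records enter it, so it is not contradicted. The conflict is between section 8.6 Step 3 and the input statement in section 8.1.

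**Conclusion.** The point holds in limited form. As worded, Step 3 builds a Period 2 dataset on which treatment is fully aliased with sequence (rank 4 of 6), so the treatment difference that Steps 4 and 5 need is not estimable. The result is algebraic: it assumes only that Step 3 is followed literally and that planned treatment follows planned sequence. It does not depend on sample size, response rates or the covariate mix.

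The reach is narrow. It covers the multiple-imputation and tipping-point analyses, which run only if dropout exceeds 20%. The primary analysis in sections 5.1 and 8.1 is untouched. This is a drafting error to correct before programming; it does not show that the SAP intends a one-period analysis.

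**What to change.** Replace the Step 3 sentence on assembling the data with: *Append the imputed Period 2 records to all observed Period 1 and Period 2 records of the high-dose FAS, then run the 8.1 model on this two-period dataset.* Naming the high-dose full analysis set matches the population that section 5.1 fixes for the primary endpoint. The Period 2 completeness check can stay.

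The cost is one sentence in section 8.6. The imputation model, the penalty steps, the pooling and the primary analysis do not change.
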